SmokefreeSGM, A Text-based Smoking Cessation Intervention for Sexual and Gender Minority Groups

NCT05029362

Version Date: 06/15/2022

This protocol describes both a pilot study and a feasibility study, which are registered as two separate records. Refer to pages 3-6, for the pilot study (aim 2) registered as ClinicalTrials.gov record NCT05645354.

Protocol Title: SmokefreeSGM, A Text-based Smoking Cessation Intervention for Sexual and Gender Minority Groups.

Principal Investigator: [name], DMD, MSc, DrPH

Co-Investigators: [name], Associate Professor in Biostatistics.

Study Coordinator: N/A

Population: Total 96 study participants (Part 2 = 30 study participants; Part 3 = 80 study participants).

Number of Sites: Single site. Data were collected in the field.

Study Duration: July 2020 to December 2023.

Subject Duration: Individual's participation will end 1 month after the smoking quit date (Part 2); Individual's participation will end 6 months after the smoking quit date (Part 3).

Funding Agency: NIH/NCI (1K22CA 237639-01A1)

Short Title: SmokefreeSGM

GENERAL INFORMATION

Smoking among sexual and gender minority (SGM) groups, which include lesbian, gay, bisexual, and transgender (LGBT) individuals, has been reported from different sources as highly prevalent (46% for gay men and 48% for lesbians). Considering that the smoking rate within SGM groups is more than double that of the general population (19%) and that smoking accounts for at least 30% of all cancer deaths, it is clear that there is an increased risk for SGM individuals to suffer from this fatal condition. Text messaging programs are effective for smoking cessation and other health behaviors. They are appealing to traditionally hard-to-reach, at-risk populations who experience barriers to smoking cessation interventions, and who have high rates of mobile phone and text messaging use, which is the case for SGM users. SmokefreeTXT is a smoking cessation intervention that sends tailored, supportive texts to users based on self-selected smoking quit date. Although this program developed by the NIH National Cancer Institute (NCI) has been successfully evaluated with the general population, no study has evaluated its feasibility specifically among SGM smokers. This protocol proposes 3 specific aims or parts:

(1) To develop SmokefreeSGM, an SGM-tailored version of SmokefreeTXT, a text-based smoking cessation program.

IRB NUMBER: HSC-SPH-20

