- 1) Individuals who are found to have a prepaid cell phone (GoPhone or pay-as-you-go plan) will be excluded,
- 2) Individuals who are found to have a cellphone number that does not work or is registered to someone else will be disqualified,
- 3) Pregnant or breastfeeding women (nicotine patches are not generally recommended to this group as nicotine can affect fetal and neonatal brain development),
- 4) Contraindication for nicotine patch. Absolute contraindications included: severe eczema or serious skin conditions, allergy to nicotine patch, pregnancy, breastfeeding, heart attack in the past 2 months, ongoing angina, peptic ulcer disease, arrhythmia, or uncontrolled blood pressure. Potential contraindications included stroke in the past 6 months, insulin therapy, and a current diagnosis of

liver, kidney or heart disease. Participants reporting an absolute contraindication are ineligible for the study. A participant reporting a potential contraindication will require that his/her primary care provider and/or other treating physician (e.g. psychiatrist) approve the nicotine patches. If the request is denied or not returned in two weeks, potential participants will be excluded from the study;

- 5) Current use of tobacco cessation medications;
- 6) Enrolled in another smoking cessation study;
- 7) Non-English speakers. Although we recognize that excluding Spanish speakers (Hispanics represent 44% of the total population in Houston)²⁴ limits the potential generalizability and reach of our text-based smoking cessation program. We do not believe that developing and delivering an SGM- tailored intervention in 2 languages is feasible within the scope of this study.
- 8) Having inadequate equipment/device (i.e., webcam, speakers, mic) for participating in telehealth sessions via Webex or Zoom AND cannot meet for an in-person screening.

Study Procedures.

Once developed, SmokefreeSGM will be beta-tested by 30 SGM adult smokers for a period of 2 weeks before and 4 weeks after their quit date.

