Recruitment procedures. Active efforts will be made to identify subjects who are suitable for enrollment into this part of the study. Flyers (Appendix B) offering help to SGM individuals interested in quitting smoking will be distributed at local community organizations and healthcare facilities working for SGM groups. We will also advertise the flyer at local newspapers, magazines, webpages, social media sites of local community organizations and healthcare facilities, and SGM-venues (e.g., bars, restaurants, etc.).

Interested individuals will contact the study team. The screening process will take place over the phone or through telehealth (e.g., Webex or a similar platform), or in person, and is divided into two parts. Part A of the screening (conducted over the phone, in person, or through telehealth) collects demographic information inaddition to an assessment of the inclusion/exclusion criteria (Appendix C). Participants who areeligible to participate in the study will be invited to complete part B of the screen (through telehealth, or in person) at a later date/time where self-reported smoking status will be verified by saliva. Informed consent will be

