delivered electronically to participants via email after they complete part A of the screening and schedule their part B screen (Appendix D). In order to avoid in-person visits, the self-reported smoking status will be objectively verified by cotinine test (either Alere or NICDetect) during screening part B (Appendix E). However in-person visits will be conducted in the circumstances that videoconferencing technology or other barriers exist for screening. Potential study participants will be mailed in advance a saliva cotinine test with instructions (delivered electronically), or provided the test in-person. During part B of the screening process, participants will conduct the test at home or in person following the step-by-step instructions provided by the research staff. The test result will be available when the colored band appears, which takes around 10 minutes. The whole procedure of objectively verifying the smoking status with the saliva test will be closely monitored during a second telehealth session. Potential study participants will be asked to show the result of the saliva test strip during the telehealth session or to the researcher in person. After enrolling into the study, participants will receive a 4-week supply of nicotine patches (NicodermCQ or CVS Health) that will be mailed to their physical address.

Baseline assessment. Immediately after confirming their eligibility and enrolling the participant into the study, additional questions will be asked to complete the baseline assessment.

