Quantitative Measures. The following data will be collected: contact information (name, email address, phone number), demographic (race/ethnicity, work status, education, marital status, number of children in household), and smoking characteristics of participants (e.g., how many smokers in the household, cigarettes smoked/day, past quit attempts, age of first cigarette use). Nicotine dependence will be measured with the Fagerstrom Test for Nicotine Dependence (FTND) at baseline. The FTND is a standard instrument for assessing the intensity of physical addiction to nicotine. The test was designed to provide an ordinal measure of nicotine dependence related to cigarette smoking. It contains six questions that evaluate the quantity of cigarette consumption, the compulsion to use, and dependence. In scoring the FTND, yes/no items are scored from 0 to 1 and multiple-choice items are scored from 0 to 3. The items are summed to yield a total score of 0-10. The higher the total FTND score, the more intense is the study participant's physical dependence on nicotine. After completing the baseline assessment, participants will receive a \$15 egift card, which will be distributed by email.

1-Month Follow-up assessment. Study participants will complete follow-up assessment via telehealth session 1 month after their quit date.

Quantitative Measures. This assessment will include the following items: contact information, sexual orientation, gender identity, living with one or more smokers in the household, cigarettes smoked/day, quitting attempts, nicotine patch use and FTND. We will also include the System Usability Scale (SUS) score which measures the usability of the SmokefreeSGM program (Appendix G). The SUS is a 10-item questionnaire with 5 response options ranging from Strongly Disagree (1) to Strongly Agree (5):

1. *I think that I would like to use this text-based smoking cessation program (SmokefreeSGM) frequently.*
2. *I found SmokefreeSGM unnecessarily complex.*
3. *I thought SmokefreeSGM was easy to use.*
4. *I think that I would need the support of a technical person to be able to use SmokefreeSGM.*
5. *I found the various functions in SmokefreeSGM were well integrated.*
6. *I thought there was too much inconsistency in SmokefreeSGM.*
7. *I would imagine that most people would learn to use SmokefreeSGM very quickly.*
8. *I found SmokefreeSGM very cumbersome to use.*
9. *I felt very confident using SmokefreeSGM.*

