10. *I needed to learn a lot of things before I could get going with SmokefreeSGM.*

For completing the qualitative measurements during the 1-month assessment, participants will receive a \$25 eGift card, which will be distributed by email.

Qualitative Approach. During the 1-month assessment, while participants are scoring the SUS items, an interviewer will be using probes (e.g., *Why do you think so?*, *What makes you feel that way?*, etc.) to elicit further information.

The entire 1-month follow-up assessment will last 45 to 60 minutes. A research staff member will act as a note-taker and will record the sessions. Findings from this mixed-method approach will indicate if the messages were perceived as interesting and appropriate. Their thoughts and feedback will be also critical for driving technical improvements of SmokefreeSGM's concept, design, and

functionality before launching it during the feasibility trial (Part 3, not presented in this protocol amendment) targeting SGM smokers who have not participated in the above-mentioned beta-test. Following completion of the 1-month assessment, participants will be mailed either a 6-week supply of nicotine patches (NicodermCQ or CVS Health) or a 4-week supply to their physical address, depending on if they are a heavy smoker (smoke > 10 cigarettes/day) or light smoker (smoke ≤ 10 cigarettes/day).

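### Part 2 mails a second nicotine patch supply after the 1-month session without a stated re-check of contraindications or patch problems

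*Combined protocol and SAP*

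**What the plan says.** All references are to the combined protocol and SAP, mainly the section on research methods for Part 2.

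- **Entry.** The exclusion criteria list absolute and potential contraindications to the patch. The rule is firm: "Participants reporting an absolute contraindication are ineligible for the study". A potential contraindication needs approval from a treating physician, and a refusal or no reply within two weeks means exclusion. Under the recruitment procedures, part A of the screening "collects demographic information inaddition to an assessment of the inclusion/exclusion criteria".
- **First supply.** After enrolment, "participants will receive a 4-week supply of nicotine patches" by mail.
- **Only follow-up.** "Study participants will complete follow-up assessment via telehealth session 1 month after their quit date". The topics listed for it include "quitting attempts, nicotine patch use and FTND", together with the System Usability Scale (SUS). The interviewer's probes accompany the SUS items.
- **Second supply.** "Following completion of the 1-month assessment, participants will be mailed either a 6-week supply of nicotine patches" if they smoke more than 10 cigarettes a day, and a 4-week supply otherwise.
- **End of participation.** Under Subject Duration in the protocol header, "participation will end 1 month after the smoking quit date (Part 2").

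**The concern.** The protocol sets a clear safety standard for giving patches and applies it before the first supply. The second supply is as long as the first or longer, yet the same standard is not visibly applied to it. The stated trigger is completion of the session. Neither current health nor tolerance of the first supply is a condition.

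What is at stake is participant safety. Conditions that would have kept a person out at entry, or required a physician's agreement, could arise between screening and the second mailing without changing what is sent. Usability, engagement and acceptability results are not at stake.

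**Working it through.** The plan gives no figure to reproduce, so the check sets its provisions side by side and adds simple timing arithmetic.

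**1. What is checked at entry (exclusion criteria).**
- Absolute: serious skin disease, patch allergy, pregnancy, breastfeeding, recent heart attack, ongoing angina, peptic ulcer, arrhythmia, uncontrolled blood pressure = 9.
- Potential: recent stroke, insulin therapy, current liver, kidney or heart disease = 3.
- Total: 9 + 3 = 12 entries, each with a stated consequence.

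**2. What is listed for the 1-month session (quantitative measures).** Contact information, sexual orientation, gender identity, smokers in the household, cigarettes per day, quit attempts, patch use, nicotine dependence score (FTND), SUS = 9 topics. Patches appear in 1 of 9 (use). Adverse effects or contraindications appear in 0 of 9. These are topic headings; the form itself (Appendix F) is not available.

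**3. Age of the entry screen.** The beta-test runs from two weeks before the quit date to four weeks after it.
- At the second mailing: 2 + 4 = 6 weeks.
- At the end of the second supply: 6 + 4 = 10 weeks (light smokers) or 6 + 6 = 12 weeks (heavy smokers).

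This assumes the full two-week pre-quit period and a second supply started straight after the session. The interval between screening parts A and B and the mailing time would lengthen these figures; an earlier quit date would shorten them.

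**4. Share of patches sent after the session.** Second supply / (first + second):
- Light smokers: 4 / (4 + 4) = 50%, or 4 × 7 = 28 days.
- Heavy smokers: 6 / (4 + 6) = 60%, or 6 × 7 = 42 days.

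**5. The two decision rules applied to the same person.**
- Became pregnant since entry: ineligible under the entry rule; mailed patches under the second-supply rule.
- Had a heart attack or developed arrhythmia since entry: ineligible; mailed patches.
- Developed a patch allergy or serious skin condition on the first supply: ineligible; mailed patches.
- Started insulin since entry: physician approval needed; mailed patches without it.

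The rules give different answers for the same clinical facts, and the stated text has no step that reconciles them.

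**The case against.** The strongest reply is that this argues from silence. Appendix F (the 1-month form), Appendix G (the interview guide) and the consent form are not in the available text. The patch-use topic may contain sub-questions on problems or reasons for stopping. A reader might infer that participants are never asked about patch problems before the second mailing. The documents do not support that. They support only that no such question, and no rule for acting on the answer, is stated in the protocol body.

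A second reply is that staff already hold a live session before mailing and ask about patch use, and the quality control section makes them available for questions during data collection. A participant who stopped because of a skin reaction may well say so. That stands, but it relies on the participant volunteering the problem. It does not prompt for pregnancy or a cardiac event, and no withholding rule follows from the answer.

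A third reply is that entry screening has already removed people who report an absolute contraindication, so only conditions arising since entry matter. That is right. The count of 12 describes the checklist, not the number of people at risk.

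A reader might also infer that the risk list under Data Safety and Monitoring is deficient because it omits the patches. The text does not bear this out. The sentence covers three named activities (the text platform, the 1-month assessment and the interviews), and its wording does not claim to be exhaustive. Patch safety is dealt with in the exclusion criteria.

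Finally, this concerns only the pilot part, which has its own registration record. That limits its reach, but Part 2 is described in this protocol and was still enrolling at this amendment.

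**Conclusion.** The concern holds in a limited form. On the stated text, the second supply depends only on completing the 1-month session, and the contraindication rules are not applied again. A participant with a contraindication or patch reaction arising since entry would still be mailed a further 28 or 42 days of patches.

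The size is modest. Thirty completers is a ceiling, because the protocol reports losses to follow-up and only completers receive the second supply. A change can help only those who have not yet passed the 1-month session. The documents give no event rate for patch problems, so the number affected cannot be estimated. No usability, engagement or acceptability result changes.

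The conclusion rests on the protocol body alone and on the beta-test schedule for the 6-week figure. If the unseen appendices already contain these questions and a rule for acting on them, a sentence in the protocol pointing to them would settle the matter.

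**What to change.** At the existing 1-month telehealth session, after the SUS and interview items and before mailing, ask about patch problems and repeat the contraindication questions used at entry. Withhold the supply for an absolute contraindication. For a potential one, require physician approval under the entry rule, including its two-week limit. Placing the questions last keeps them from influencing the usability responses.

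The cost is a few minutes in a session already described as follows: "The entire 1-month follow-up assessment will last 45 to 60 minutes". It also needs a short protocol amendment. Anyone newly needing physician approval could wait up to 2 weeks for the second supply. If patches were started on the quit date (an assumption, as the documents give no start date), the first 4-week supply would be finishing at about that time, so the wait could interrupt patch use. No endpoint, visit or sample size changes.

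A follow-up text during the second supply, with a longer Subject Duration, is not recommended. It would need the platform kept open, and its messages would enter the engagement count of texts sent and received unless they were excluded. That is out of proportion to a risk that cannot be sized from the documents.
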